3.2 Adherence and Protocol Deviations

Both experimental arms (COV.EXPECT, COV.SUPPORT) receive three individual online video consultation sessions with an interval of 2 weeks with given homework after each session and a booster session after 3 months, each lasting 45 minutes. The adherence to the intervention is evaluated based on the number and duration of attended online sessions.

Major protocol deviations will lead to exclusion of a subject from the Per Protocol Population (see Section 3.3.2). Major protocol deviations are any unapproved changes in the research study design and/or procedures that are within the investigator's control and not in accordance with the independent ethics committee (IEC) / institutional review board (IRB) - approved protocol that may affect the subject's rights, safety or well-being, or the completeness, accuracy and reliability of the study data.

Protocol deviations (PD) are defined as follows:

Major PDs:

- Violation of in- and exclusion criteria
- PHQ-15 < 10 in the baseline assessment (in deviation from the inclusion screening)
- At 3-month follow-up:
 - More than 1 missing intervention session (COV.EXPECT, COV.SUPPORT)
 - More than 1 substantially shortened intervention session (< 30 minutes session time)

Additionally, there will be a blind review of a list of further detected protocol violations. The principal investigator will decide which reported protocol violations are considered major and potentially impact the study results.

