5.3.5 Sensitivity Analyses

The primary analysis (mixed linear model based on implicit MAR assumptions) will be repeated in the PP set. Furthermore, for the primary analysis a multiple imputation procedure will be conducted in case more than 5% of values are missing for the primary outcome.

Also, a potential effect of recruitment setting will be investigated by including setting as a fixed effect in the primary analysis model.

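### Missed and shortened sessions are counted separately in the per-protocol definition, so attending less can restore a patient's per-protocol status

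*SAP*

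**What the plan says.** Section 3.2 states that both experimental arms "receive three individual online video consultation sessions with an interval of 2 weeks" and "a booster session after 3 months, each lasting 45 minutes". It then gives the adherence principle: "The adherence to the intervention is evaluated based on the number and duration of attended online sessions".

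Among the major protocol deviations assessed at the 3-month follow-up are two session criteria, listed as separate bullets: "More than 1 missing intervention session (COV.EXPECT, COV.SUPPORT") and "More than 1 substantially shortened intervention session (< 30 minutes session time"). The consequence is stated in the same section: "Major protocol deviations will lead to exclusion of a subject from the Per Protocol Population". No criterion adds missed and shortened sessions together, and none sets a minimum total contact time.

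For other deviations, "there will be a blind review of a list of further detected protocol violations", after which the principal investigator decides which are major.

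The PP set is used in section 5.3.5: "The primary analysis (mixed linear model based on implicit MAR assumptions) will be repeated in the PP set". Section 5.1.1 also describes baseline characteristics in it.

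**The concern.** An adherence rule should not become easier to satisfy when a patient attends less. Because each lapse has its own counter and each counter tolerates one lapse, replacing a short session by no session moves that lapse to the other counter, where it is tolerated.

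The repeat of the primary model in the PP set is the only adherence-based check of the treatment effect in the SAP. If membership can be regained by skipping a session, the set is less clearly one of patients who received the intervention, and that blurs what the sensitivity analysis shows.

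**Working it through.** The SAP gives no figure to reproduce here beyond its thresholds, so the check applies the written rule to every attendance pattern.

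**Inputs (all section 3.2).** Three regular sessions and one booster; 45 minutes each; major deviation if missed > 1 or shortened (< 30 minutes) > 1. Planned contact is 3 × 45 = 135 minutes, or 4 × 45 = 180 minutes if the booster counts. Assumptions: whole minutes, no session longer than planned, a missed session is 0 minutes, and a shortened session is one that was held (1 to 29 minutes).

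**Step 1: one patient, third session varied.** Hold two sessions at 45 and 20 minutes and let the third last t minutes.

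| t | Missed | Shortened | Total minutes | Rule as written | Combined count (missed + shortened > 1) |
|---|---|---|---|---|---|
| 0 | 1 | 1 | 65 (65/135 = 48%) | kept | excluded |
| 1 to 29 | 0 | 2 | 66 to 94 (49% to 70%) | excluded | excluded |
| 30 to 45 | 0 | 1 | 95 to 110 (70% to 81%) | kept | kept |

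As written, status runs kept, excluded, kept as attendance rises. The same happens whenever the other two sessions are one adequate (30 minutes or more) and one shortened. Under the combined count status changes once, at 30 minutes.

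**Step 2: all patterns.** Enumerating every combination of missed, shortened and adequate sessions, the written rule and the combined count disagree on one pattern only, exactly one missed plus one shortened. This holds for three sessions and for four. With three sessions that pattern carries 31 to 74 minutes (1 + 30 to 29 + 45), at most 74/135 = 55% of plan. With four it carries 61 to 119 minutes.

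**Step 3: comparison between different patients.** Compare a kept patient (one missed, one shortened, one full) with an excluded patient (two shortened, one full):

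- Largest gap in favour of the excluded patient: (29 + 29 + 45) − (0 + 1 + 45) = 103 − 46 = +57 minutes.
- Largest gap the other way: (1 + 1 + 45) − (0 + 29 + 45) = 47 − 74 = −27 minutes.
- If shortened sessions were uniform on 1 to 29 minutes (illustrative only; the SAP gives no distribution), the excluded patient has more minutes in 83% of pairs, on average by 15 minutes.

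**Step 4: what the combined count leaves in place.** 0 + 45 + 45 = 90 minutes has one lapse and is kept; 29 + 29 + 45 = 103 minutes has two and is excluded. The combined count removes the reversal in Step 1 but does not order patients by total minutes.

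**The case against.** - **Each criterion is explicit and programmable, and one lapse of each kind may be intended.** This stands in part. How strict a PP set should be is a design choice, and the SAP sets no total-minutes requirement that the rule violates. Tolerating one lapse of each kind does not explain, however, why a patient should qualify by staying away from a session and not by attending part of it.
- **A missed session lasts 0 minutes and so already counts as under 30.** On that reading two missed sessions would always break the second criterion and the first would be redundant. Separate bullets and the word shortened point to sessions that were held. If the other reading is meant, the text needs the same clarification.
- **The blind review could class one missed plus one shortened session as major.** It could, but by discretion and not by a fixed rule. No route is given for re-admitting the patient excluded for attending part of a session.
- **A stronger reading.** A reader might infer that the rule generally ranks low contact time as adherent and high contact time as non-adherent. The SAP does not support that. Between patients the difference runs in both directions (−27 to +57 minutes), and total minutes is not the SAP's yardstick. Only the within-patient reversal follows from the text without further assumptions about session lengths.

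**Conclusion.** The point holds as a defect in the PP definition. As written, one missed plus one shortened session is per protocol, while attending part of the missed session would exclude the same patient. That is at odds with section 3.2's own adherence principle. It rests on reading the two bullets as separate counts, which is the reading that gives each of them a purpose. The reversal does not depend on the booster, but the percentages do: the 135-minute base assumes the booster is not counted, and the SAP does not say whether a session held after 3 months enters an assessment made at the 3-month follow-up.

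The importance is minor. The primary analysis uses the full analysis set (sections 3.3.1 and 5.3.1), so the primary result is untouched. What is affected is the PP sensitivity analysis and the PP baseline description. The number of patients with the pattern, and so any shift in the PP estimate, cannot be derived from the SAP.

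**What to change.** In section 3.2, replace the two session criteria by one for the PP definition: more than one session that is either missing or under the existing 30-minute threshold. In the same line, state whether the booster is among the sessions counted at the 3-month assessment. This reconciles the two bullets using the SAP's own threshold; whether that threshold is the right one is not judged here.

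With three sessions counted, every PP patient in the experimental arms would then have at least two sessions of 30 minutes or more; at present one is enough. If the sponsor wants membership to follow total contact time, a rule on minutes would be needed, because the combined count does not provide that (Step 4).

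The cost is one line in an SAP amendment, with no new data, since the number and length of sessions are already needed. The downside is that patients with one missed and one shortened session leave the PP set; these are probably few, but the SAP does not allow a count. The change is best made before patients are classified for the PP set.

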3.3 Analysis Populations

Depending on the type of analysis, different analysis populations will be used which are defined in detail in this section.

3.3.1 Full Analysis Set (FAS)

The primary analysis is based on the full analysis set (FAS). The FAS is as complete as possible and as close as possible to the Intention-To-Treat (ITT) principle which includes all randomised patients, as belonging to their randomisation arm, regardless of whether they refused therapy, or whether other protocol violations are known.

3.3.2 Per Protocol Population (PP)

The Per Protocol population (PP) is a subset of the FAS and includes only patients who have no major protocol violation. Patients are analyzed as belonging to the randomised treatment group.

Version 1.0 Page 10 of 18

3.3.3 Evaluated for Safety Set (EFS)

The Evaluated for Safety (EFS) set consists of all randomised patients. Subjects are analysed as belonging to their randomised arm according to the ITT principle.

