2.2 Randomisation

Patients are randomised to COV.EXPECT, COV.SUPPORT or TAU with an allocation ratio of 1:1:1. The randomisation is stratified by sex with a block randomisation procedure with varying block length. The randomisation list was generated using R software (R Project for Statistical Computing) by an independent member of the biostatistics unit and uploaded in REDCap (Research Electronic Data Capture), a software for building and managing online surveys and databases.

The randomisation is performed directly after verification that no inclusion criteria are violated and no exclusion criteria are met. Baseline data are collected afterwards.

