5.4 Safety Evaluation

Adverse events (AE) and serious adverse events (SAE) are analysed descriptively, i.e. event rates with percentages on patient level and event numbers on event level will be given in total and by randomised treatment in the EFS.

Version 1.0 Page 16 of 18

All AEs are reported, whether or not they are considered to be related to treatment. If not stated otherwise, AEs are counted over the complete trial duration, i.e. from randomisation up to 6 months.

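### The only planned adverse event tables keep never-starters in the experimental arms, which shrinks any excess of harm; one supplementary started-only table would show by how much

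*SAP*

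**What the plan says.** Section 3.3.3 of the SAP defines membership of the safety set without any condition on treatment: "The Evaluated for Safety (EFS) set consists of all randomised patients". On grouping it adds: "Subjects are analysed as belonging to their randomised arm according to the ITT principle". Section 3.3.1 shows what the SAP means by that principle, since patients stay in their arm "regardless of whether they refused therapy, or whether other protocol violations are known".

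Section 5.4 plans descriptive safety reporting only. Patient-level percentages and "event numbers on event level will be given in total and by randomised treatment in the EFS". Causality does not filter the events: "All AEs are reported, whether or not they are considered to be related to treatment". The window is the same for all arms: "AEs are counted over the complete trial duration, i.e. from randomisation up to 6 months".

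Section 3.2 shows that information on exposure will exist: "The adherence to the intervention is evaluated based on the number and duration of attended online sessions". The per-protocol set, which does use attendance, serves the baseline tables (5.1.1) and an efficacy sensitivity analysis (5.3.5). It is not used for safety.

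**The concern.** For efficacy, keeping refusers in their arm is cautious because it pulls the arms together. For harm, the same pull hides part of a real excess. A patient who attends no session cannot be harmed by the sessions, yet still counts in the denominator of the experimental arm.

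The effect is one-sided. TAU patients have no study session to decline, so only COV.EXPECT and COV.SUPPORT are diluted. The SAP expects some non-attendance: 3.3.1 provides for refused therapy and 3.2 for missed sessions. Section 2.2 places baseline data collection after randomisation, so a patient can leave before any session.

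At stake is how the safety tables are read. Similar AE percentages across arms could reflect well-tolerated sessions or sessions that some patients never had. The planned tables alone do not separate the two.

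**Working it through.** **Patients per arm, from the SAP.** Section 2.3 gives d = 0.5, two-sided alpha 5% and power 80%. The two-sample t-test calculation gives 63.77, rounded up to the stated 64 per group. With 25% loss to follow-up, 64 / (1 − 0.25) = 85.3, rounded up to 86 per arm; 3 × 86 = 258, the stated total. The 1:1:1 allocation in 2.2 fits this. The sample size is not in dispute and only supplies the 86.

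**Assumptions, not from the SAP.** Let u be the share of an experimental arm that never starts. Assume an AE risk of 10% in TAU and 20% in patients who start, so a true excess of 10 points. The 25% in 2.3 is loss to follow-up by 3 months and is not a never-starter rate.

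**Dilution.** If never-starters have the TAU risk:

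observed rate = (1 − u) × 20% + u × 10%

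observed excess = observed rate − 10% = (1 − u) × 10 points

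If never-starters are also lost and report no AEs:

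observed excess = (1 − u) × 20% − 10%

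| u (assumed) | Starters out of 86 | Rate in arm | Excess, never-starters at TAU risk | Excess, never-starters report nothing |
|---|---|---|---|---|
| 0% | 86 | 20.0% | 10.0 points | 10.0 points |
| 5% | about 82 | 19.5% | 9.5 points | 9.0 points |
| 10% | about 77 | 19.0% | 9.0 points | 8.0 points |
| 20% | about 69 | 18.0% | 8.0 points | 6.0 points |

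In a table restricted to starters the excess stays at 10 points under the same assumptions.

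**Rare events.** If an arm has no serious adverse event, the exact upper limit (two-sided 95%) is 1 − 0.025^(1/n). For n = 86 it is 4.2%. For 86 × 0.8 ≈ 69 starters it is 5.2%. The SAP does not plan such limits; they only show how much less the data say about patients who attended.

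**Time origin of an added table.** Suppose events were counted from the first session in the experimental arms but from randomisation in TAU. Assume a first session at week 2 of 26 and a constant background hazard that gives 10% over 26 weeks. Background hazard over 2 weeks = −ln(0.9) × 2/26 = 0.0081. The experimental rate becomes 1 − 0.8 × exp(0.0081) ≈ 19.4% instead of 20%. About 0.65 points of excess disappear, which lies between the dilution at u = 5% (0.5 points) and at u = 10% (1.0 point). Unequal windows would therefore bring in an error of similar size and in the same direction.

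**The case against.** The choice is explicit, and 3.3.3 and 5.4 agree with each other. TAU has no first session, so randomisation is the only starting point shared by all arms. An as-randomised table keeps the arms comparable and loses no event. That stands, and it is why this table should remain the main one.

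The size of the effect is wholly assumed and small against the noise. At 10% versus 20% with 86 per arm, the 95% half-width of the difference is 1.96 × √(0.10 × 0.90/86 + 0.20 × 0.80/86) ≈ 10.6 points, while the dilution is 0.5 to 2.0 points. That also stands. Dilution, however, is systematic and always in one direction, and data that 3.2 already calls for would make it visible.

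The SAP softens the problem in part. Adherence is evaluated (3.2), and drop-outs are reported with timing and reason by arm (4.3, 4.4). A reader could gauge non-attendance from these, but could not link it to the events.

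Four stronger readings are tempting, and the document does not support them:

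- *Never-starters are presented as exposed.* Section 5.4 tabulates by randomised treatment and does not call the denominator exposed.
- *The safety set merely duplicates the full analysis set.* Section 3.3.1 only brings the full analysis set as close as possible to intention-to-treat, while the safety set takes every randomised patient without condition. The primary model in 5.3.1 needs baseline PHQ-15, so the safety set can hold patients whom that model cannot use.
- *Counting from randomisation is an error because it mixes events before and after the first session.* The common window is what makes the arms comparable.
- *The trial will claim safety from an absence of excess.* No safety test, interval or claim of that kind is planned.

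**Conclusion.** The point holds as a gap in reporting. The planned AE tables show only the as-randomised view, in which any excess in COV.EXPECT or COV.SUPPORT shrinks by the never-starter share. An assumed 10-point excess shows as 9.5, 9.0 or 8.0 points at 5%, 10% or 20%. It would fall further if never-starters also stop reporting events.

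This rests on three assumptions: the never-starter share, the AE rates, and never-starters having the TAU risk. The SAP supplies none of them. If nearly everyone starts, the two tables will almost coincide, which would itself be useful to show. The primary analysis is untouched and no formal safety comparison is affected. The as-randomised safety set is not wrong; it needs a companion.

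**What to change.** Keep the as-randomised table as the main safety table, with its window from randomisation to 6 months. Add to 3.3.3 and 5.4:

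- one supplementary descriptive table of AEs and serious AEs, restricted in COV.EXPECT and COV.SUPPORT to patients who started at least one session, with TAU as randomised and the same window from randomisation in all arms;
- the number of never-starters in each experimental arm, shown beside both tables;
- a separate listing of events in never-starters and of events before the first session. Events of starters before their first session stay in the supplementary table as well, so that the windows remain equal.

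The cost is a few lines of SAP text and one extra table. Session attendance is already to be evaluated under 3.2. The listing also needs the date of the first session and the onset dates of AEs; the SAP does not name these, so their availability should be confirmed. The downside is that starters are self-selected and must have stayed in the trial up to a first session. The supplementary comparison with TAU is therefore not randomised, and the table should say so.

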3.4 Missing Data

3.4.1 Description of missing data

Missing data on the primary and secondary endpoints (at baseline and follow-up time points) will be summarised by absolute and relative frequency (i.e. the number of patients with missing values divided by all patients and multiplied by 100) of missing values by treatment group and in total.

3.4.2 Handling of missing values

Missing values in the primary endpoint (missing total score of PHQ-15) will not be replaced for the primary analysis. Yet, for the analysis of the primary endpoint, the implicit "missing at random" (MAR) assumption of the mixed model will be utilised.

If more than 5% of values are missing for the primary outcome, we will use multiple imputation in a sensitivity analysis after final database lock with 100 imputations (White et al., 2011).

Version 1.0 Page 11 of 18

4 Description of Subject Flow (for CONSORT flow diagram)

In this chapter, details on how subjects flow from screening to the end of study is summarised are given.

4.1 Screening, Eligibility and Randomisation

The number of subjects screened, the number of screening failures (ineligible subjects), the number of eligible subjects who were not randomised and the number of eligible subjects who were randomised will be summarised by absolute and relative (%) frequencies and displayed in the CONSORT (Consolidated Standards of Reporting Trials) flow chart (see section 4.4).

4.2 Analysis Populations

The number of patients in the FAS, PP and EFS set will be given in total and by randomised treatment.

4.3 Withdrawal / Follow-up

The number and percentage of patients who withdraw their consent, who were lost to follow-up and who dropped out due to death will be summarised in total and by randomised treatment in the FAS, including information on time of drop-out and the reason for drop-out, if available.

4.4 CONSORT flow chart

A flow chart according to CONSORT statement will be given which will include the number of subjects

- Screened
- Not eligible (with reason)
- Eligible and not included (with reason)
- Randomised
- Allocated to treatment groups
- Withdrawals (with timing and reason by treatment group)
- Dropouts (with timing and reason by treatment group)
- Analysed after 6 weeks, 3 months and 6 months (by treatment group)

Version 1.0 Page 12 of 18

5 Analysis

In this chapter, the analysis of baseline data as well as efficacy and safety endpoints is described in detail.

5.1 Descriptive statistics

Continuous data will be summarised by arithmetic mean, standard deviation, minimum, 25% quantile, median, 75% quantile, maximum, and the number of available (non-missing) observations. If appropriate, continuous variables can also be presented in categories.

Categorical data will be summarised by the total number of patients in each category and the number of patients with non-missing values. Relative frequencies are displayed by the percent relative to non-missing values (100 times the number of patients per category divided by the number of patients with non-missing values).

5.1.1 Demographics and Baseline Characteristics

The following demographic and other baseline characteristics will be summarised in total and by randomised treatment as described in 5.1 in the FAS and PP set:

- Age in years
- Gender (male/female/divers)
- Duration of Long COVID
- Number of SARS-COV-2 infections
- Treatment setting of SARS-CoV-2 infections (At home, outpatient/At least one time in hospital on a normal ward)
- Number of SARS-COV-2 vaccinations
- Number of pre-existing physical conditions (Self-Administered Comorbidity Questionnaire [SCQ-D])
- Body mass index in kg/m²
- Migration background (yes/no)
- Permanent partner (yes/no)
- Number of people living in household
- Years of formal education (Lower education/Higher education)
- Occupational status (Full-time employed/Part-time employed/Stay-at-home/Unemployed or job seeking/Retired (pension)/Retired (disability)/School, training, studying/Parental leave/Other)
- Current sick leave (No/Yes, shorter than 6 weeks/Yes, longer than 6 weeks)
- Number of appointments with the doctor in the last 6 months
- Current intake of medication (yes/no)
- Smoking (yes/no)
- Recruitment channel (UKE/Self-help group/Social media/Online search/Medical practitioner/Physiotherapy practice/Friends, acquaintances/Other)
- Overall somatic symptom severity (PHQ-15)
- Long COVID symptoms (PHQ-15 PAIS)
- Fatigue (CFS)
- Post-exertional malaise (DSQ-PEM)
- Pain (PDI)
- Illness-related anxiety (SSD-12)
- Treatment expectations (TEX-Q)
- Expectation of symptom severity (NRS)
- Expectation of symptom burden (NRS)
- Expectation of coping with symptoms (NRS)

Version 1.0 Page 13 of 18

- Depression severity (Patient Health Questionnaire-9 [PHQ-9])
- Anxiety severity (Generalized Anxiety Disorder-7 [GAD-7])

